5.6.1 Pregnancy Testing and Birth Control

Women of child-bearing age are eligible subjects for this study. However, since study drugs are pregnancy rate "D" (losartan) and "C" allopurinol, female subjects will take a urine pregnancy test at Visit 1 to ensure they are not pregnant. A urine pregnancy test will be repeated at Visit 1A if the study visit occurs more than 90 days after Visit 1. Furthermore, a urine pregnancy test will also be given at Visit 3 prior to study drug dispensing. The Pregnancy and birth control case report form should be completed at Visit 1, Visit 1A (if applicable) and Visit 3. On this case report form the method of birth control used should be documented and subjects are instructed to keep their birth control consistent throughout the study. Methods of birth control that are acceptable while participating in this study include oral contraceptives, hormonal contraceptives, hormonal implants, contraceptive patches, NuvaRing, intrauterine device hormonal, intrauterine device non-hormonal, barrier method, spermicide, post-menopausal for greater than or equal to two (2) years, tubal ligation, bilateral oophorectomy, or hysterectomy, vasectomy, or abstinence. If a female is practicing abstinence, she should confirm this, including duration, and initial and date the case report form.

5.7 *Blinding of Study Drug*

Allopurinol and Losartan tablets will be over encapsulated and dispensed to subjects with a placebo using a double-dummy design. Both subjects and investigators will be blinded to study drug assignment. The PRC will have unblinding information should the need arise to unblind a subject's study drug assignment. To obtain unblinding information, please call the University of Wisconsin Pharmaceutical Research Center at [contact].

5.8 *Receiving, Storage, Dispensing and Return*

5.8.1 Receipt of Drug Supplies

The PRC will order, receive and store all study medications for the trial. The PRC complies with all Federal and State regulations and current good manufacturing practices.

5.8.2 Dispensing of Study Drug

The PRC performs all required study drug reconciliation and inventory procedures on a regular basis. PRC drug record logs record the movement of study drugs out of PRC storage and all medications are checked by a PRC pharmacist prior to dispensing to the subject and study staff. Amount of study drug on hand and dispensed is constantly tracked in PRC records. All study drugs will be dispensed by the PRC to subjects during Visit 3 in Madison. Subjects will receive all study drugs for the 6-week treatment period at Visit 3 and will receive instructions from investigators prior to starting therapy. Zolpidem (supplied by the PRC) will be given to subjects upon discharge from the CRU at VISITS 3 and 6 to be taken immediately before (9-10pm) the control of breathing study on night two.

6 Study Procedures

See Appendix 2

6.2 Summary of Visits

Subjects may complete some, but not all procedures without a protocol deviation occurring or affecting their study eligibility. For logistical or other reasons, subjects may complete some of the procedures (but not all procedures) (i.e. in cases of non-exclusionary subject disabilities that preclude them from having certain procedures done or body habitus that does not allow completion of certain procedures.). Reimbursement for participation will be pro-rated for Visits 3 and 6 as in protocol section 11.2.

Visit 1: Screen Visit (will be performed at each respective recruitment site)

- informed consent, height and weight, heart rate, blood pressure, temperature, and electrocardiogram recorded, blood samples, urine pregnancy test, brief history (performed by study coordinator and local PI)
- physical examination (local PI and UWHC medical staff (i.e., physician, physician's assistant, or nurse practitioner) for Madison subjects)

Visit 1A: If visit 2 will occur more than 90 days after visit 1, subjects will undergo repeat screening procedures in a separate visit to the local study site (Visit 1A) including:

Medical history, medication history, birth control assessment, blood samples, urine pregnancy test, AE assessment, electrocardiogram recorded (performed by the local PI, study coordinator, or medical staff (i.e., physician, physician's assistant, or nurse practitioner)

Visits 2 and 5: Home Blood Pressure Monitoring (will be performed at each local site where subjects were originally enrolled)

- Receive blood pressure monitor and Holter/heart rate variability monitor* to wear for 24 hours along with the diary recording of activity each time they engage in activity and each time the blood pressure cuff inflates; subject returns to the study site the following day (all activities performed by coordinator-local PI consulted if necessary). Subjects at UW-Madison will come to the School of Pharmacy Clinical research space of the Office of Clinical Trials Examination Space (H6/136 CSC) to be set up with their 24-hour blood pressure cuff and Holter/heart rate variability monitor. Adverse events will be assessed at visits 2 and 5.

Version: 23, 7-25-17

*Holter and Heart rate variability measurements are optional and will only be offered to UW subjects. They can choose to opt-in or opt-out of those procedures. Subjects who are non-CPAP users will have Holter monitoring done at Visits 3 and 6, but will not have Holter monitoring performed at Visits 2 and 5." The Holter monitors will be connected by UW Sleep Laboratory Technicians or study team personnel. Subjects may disconnect the Holter monitor on their own, or they may come back to UW-Madison to have the Holter monitor removed. A postage-paid envelope will be provided to subjects to return to Holter monitor by mail.

Visits 3 and 6: (each visit requiring a one or two night stay in Madison at the CRU at UW and the VA Hospital for all subjects enrolled in the study)

- Day 1: Vital signs, Heart Rate; Forearm Blood Flow; Blood Samples; Cerebral blood flow; Nerve activity; Reduced oxygen exposure and increased oxygen breathing; overnight sleep study and heart rhythm measurements at the CRU to measure brain waves, respiration, blood oxygen level, snoring, leg movements, heart rhythm, and heart rate variability* (performed by PIs and sleep technician). A physical exam will also be obtained. If bruit are noted on physical exam the subject will no longer be able to participate in the study. The presence of a bruit would potentially indicate previously unrecognized cardiovascular disease.
- Day two: Ultrasound of blood vessels and heart; non-invasive tonometry; assessment of CPAP use; assessment of daytime sleepiness by completing the Epworth sleepiness scale; Study Medication dispensation (V3) and collection (V6); Control of Breathing Experiments during sleep stay at VA hospital. Subjects will receive zolpidem (sleeping medication) upon discharge from the CRU to be taken around 10pm at the start of the control of breathing study. (Ultrasounds performed in [name] laboratory; control of breathing studies performed by sleep technician). Subjects who do not have someone to drive them home, do not want to take a complimentary cab home or do not want to go back to the CRU to sleep and have breakfast prior to having a driver/cab take them home from Visits 3 and 6 may opt out of the control of breathing study on the second night. When a subject arrives for Visits 3 and 6, he/she will be asked if they have a driver to take them home, need a cab ride home or if they agree to go back to the CRU to sleep and have breakfast prior to having a driver/cab take them home after the control of breathing study.
- Visit 6 will also include AE Assessment and diary review in addition to the procedures mentioned above.

*Holter and Heart rate variability measurements are optional and will only be offered to UW subjects. They can choose to opt-in or opt-out of those procedures. Subjects who are non-CPAP users will have Holter monitoring done at Visits 3 and 6, but will not have Holter monitoring performed at Visits 2 and 5." The Holter monitors will be connected by UW Sleep Laboratory Technicians or study team personnel. Subjects may disconnect the Holter monitor on their own, or they may come back to UW-Madison to have the Holter monitor removed. A postage-paid envelope will be provided to subjects to return to Holter monitor by mail.

Visit 4: Monitoring visit (performed at each local site where subject was enrolled)

- measurement of blood pressure, heart rate, temperature, and height and weight, blood sample collection, Study drug compliance and diary review, AE assessment (all performed by local site coordinator or CRU nurses for Madison subjects)

Visit 7: One month Follow-up (performed at each local site where subject was enrolled)

- Subjects will be contacted by phone for completion of a final AE assessment (performed by local site coordinator)

6.3 Sample collection

Blood samples collected during Visits 1 and 4 will be processed for the specific laboratory parameter at the local site and assayed in the clinical labs (or couriered from LaCrosse to Marshfield to be assayed). Samples will be collected and sent to the clinical laboratory for measurement of serum creatinine, serum potassium, serum glucose, lipid panels, serum uric acid, etc. At Visits 3 and 6 at UW-Madison, blood samples will be drawn at rest while the subject is breathing room air. Uric acid will be collected and assayed in the UW Hospital and Clinics Clinical Laboratory and other samples will be collected for research use. These samples collected for research use will be centrifuged, aliquoted, and stored in the locked freezer space at the University of Wisconsin School of Pharmacy for future assay. Stored blood samples will be stripped of identifiers and only labeled with study subject number and Visit number. Plasma will be sent to the TTR Analytical Laboratory Core at the University of Iowa College of Pharmacy for plasma catecholamine measurement. Other plasma will be assayed at the UW School of Pharmacy for oxidative stress markers.

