3.2 Primary Study Endpoints

The primary outcome variable is the difference in the individual slope of the MSNA – SaO₂ response curve at 6 weeks and baseline between treatment groups. Basal normoxic MSNA and MSNA responses during hypoxia will be compared between the three treatment groups. For purposes of quantification, MSNA is expressed as burst frequency (bursts/min), burst amplitude (arbitrary units) and total minute activity (burst frequency x mean burst amplitude). Total minute activity of mSNA is an effective way to capture the change in both burst frequency and burst amplitude. Both amplitude and burst frequency are influenced by disease states such as OSA and by environmental conditions such as hypoxia. Postganglionic mSNA in the right peroneal nerve will be recorded directly using the microneurography technique (95). The neural signals are passed to a differential preamplifier, an amplifier, a band-pass filter, and an integrator (time constant=100 ms). Placement of the recording electrode within a muscle nerve fascicle is confirmed by the presence of muscle twitches in response to electrical stimulation, the appearance of afferent activity in response to tapping or stretching of muscle, but not gentle stroking of skin, in the appropriate receptive fields, and other criteria. Once an acceptable neural recording (signal-to-noise ratio >3:1) is obtained, the subject is instructed to maintain the leg in a relaxed position for the duration of the study. Sympathetic bursts will be identified by computer-assisted inspection of the mean voltage neurogram.

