5.4 Preparation and Administration of Study Drug

Study drug will be over encapsulated by the University of Iowa Pharmaceuticals (UIP) and stored and distributed by the University of Wisconsin Pharmaceutical Research Center and blinded according to a pre-designed scheme. Subjects will be randomized at the end of visit 1 (screening visit) and will receive study drug at their baseline physiology study visit (visit 3). UIP is an FDA-registered facility compliant with 21 CFR parts 11, 210, and 211, licensed by the DEA to handle controlled substances (Schedules I-V), and capable of handling potent/cytotoxic materials. UIP has been a cGMP facility for over 30 years.

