5.5 Subject Adherence Monitoring

All subjects will receive instructions on how to take and record medication adherence in a diary. Subjects will not receive study medications until the end of the Physiology Visit in Madison (Visit 3) and will be instructed to bring their study medications with them to Visit 4 (two weeks after starting medication at local study site) and Visit 6 (Six weeks after starting study medication – in Madison). Serum uric acid concentrations and plasma renin activity will be measured at baseline and after 6 weeks of study medication and will provide an indirect measure of drug adherence in subjects receiving allopurinol and losartan. Adherence to CPAP therapy will be monitored at Visit 4 (two weeks after starting medication) and Visit 6 (Six weeks after starting study medication). CPAP adherence can be determined from the electronic data card in the CPAP machine and downloaded into a printable report. Each site will have a card reader and software for

Version: 23, 7-25-17

downloading the information from subjects' CPAP machines at Visit 4. Subjects on BiPAP will use their machines instead of ours, and we will attempt to get their adherence data from them.

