9.4 Data Collection at Sites

Data will be collected at Marshfield Clinic, Gundersen Health System, and Aurora Bay Care at the screening visit (Visit 1) and subject monitoring visit (Visit 4). In addition, 24-ambulatory blood pressure monitoring will be performed at each site (Visits 2 and 5). Data from these visits including subject demographic information, vital signs, laboratory test values, and other subject information will be uploaded into OnCore CRM clinical trial software. As a result all investigators will be able to access subject data from the screening visit and monitoring visit. It is vital that all investigators can access data from the monitoring visit for safety reasons and monitoring of the study medications. Data for the primary outcome variable will be uploaded into OnCore from Visit 3 and Visit 6 and will be made available for the data and safety monitoring committee when they meet quarterly and for interim/final analyses after 33%, 66%, and 100% of subjects have been enrolled.

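### On-treatment uric acid, the plan's own allopurinol marker, goes through clinical laboratories and is not stated to be withheld from investigators or burst scorers

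*Combined protocol and SAP*

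**What the plan says.** - **Marker.** Section 5.5: "Serum uric acid concentrations and plasma renin activity will be measured at baseline and after 6 weeks of study medication". The two tests "will provide an indirect measure of drug adherence in subjects receiving allopurinol and losartan".
- **Visits 1 and 4.** Section 6.3: "Blood samples collected during Visits 1 and 4 will be processed for the specific laboratory parameter at the local site". Clinical laboratories then run the assays. The next sentence gives one list for these samples: "serum creatinine, serum potassium, serum glucose, lipid panels, serum uric acid, etc".
- **Visits 3 and 6.** Section 6.3: "Uric acid will be collected and assayed in the UW Hospital and Clinics Clinical Laboratory". The other samples from these visits are stripped of identifiers, coded and frozen for later assay.
- **Access.** Section 9.4 puts site laboratory values into the trial database, with the consequence that "all investigators will be able to access subject data from the screening visit and monitoring visit".
- **Blinding.** Section 5.7 commits to blinding both subjects and investigators. Section 7.2 adds a blinded statistician.
- **Primary outcome.** Section 3.2: "Sympathetic bursts will be identified by computer-assisted inspection of the mean voltage neurogram". Section 6.2 has the Day 1 measurements at Visits 3 and 6, nerve activity among them, carried out by the principal investigators and a sleep technician.

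**The concern.** A test that indicates whether a subject is taking allopurinol also indicates who was assigned to it. The plan sends that test through the ordinary clinical route and does not say that on-treatment results are kept from the people who run the study or score the recordings.

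Burst identification needs human judgement, and the primary outcome is a slope built from those bursts. A scorer who knew or guessed the arm could shift the allopurinol slopes without meaning to, and blinding the statistician downstream would not remove that shift.

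The plan otherwise guards its blind with care: over-encapsulation, two bottles in every arm, and creatinine and potassium checks in all subjects so that monitoring does not reveal losartan. Uric acid is the arm-specific test left outside those safeguards.

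**Working it through.** The point concerns access to information. The plan states no figure to reproduce, so the check sets the sections side by side.

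**1. Which results are on treatment?** Section 5.4 randomises at the end of Visit 1 and gives drug at Visit 3. Visit 1 and Visit 3 values are therefore pre-drug; Visit 4 (week 2) and Visit 6 (week 6) values are on treatment. Uric acid is also measured at screening (section 4.3), and screening data are open to investigators, so a subject's own comparator is available.

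**2. Is uric acid run at Visit 4?**

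| Section | What it implies for Visit 4 |
|---|---|
| 6.3 | Uric acid is in a list that covers Visits 1 and 4 together |
| 3.1 | Safety bloods named are creatinine and potassium only |
| 5.5 | Uric acid is timed at baseline and week 6 only |

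These do not agree. The pooled list in 6.3 resembles the screening panel in 4.3, so it may describe Visit 1 alone, but it does not say so.

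**3. Who can see the result?**

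| Visit | Where assayed | Stated access |
|---|---|---|
| 4 | Clinical labs, if run | All investigators (9.4) |
| 6 | Hospital clinical laboratory (6.3) | Not stated |

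The Visit 6 upload described in 9.4 is the primary-outcome data, for the monitoring committee and the interim and final analyses. Section 6.5 provides for letters to subjects about unexpected serum laboratory findings. That implies someone reviews laboratory results, and uric acid is not exempted.

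**4. Who produces the primary outcome?** Investigators take part in the recordings (6.2), and bursts are scored with human inspection (3.2). No available text masks scorers to arm, visit or laboratory results.

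**5. Scale, for illustration only.** The documents give no size for a scoring bias, so the shifts below are assumptions. Inputs from section 7.1: difference 3.07, 20 subjects per group, two-sided alpha 0.017, power 90%.

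- Implied SD = 3.07 / [(2.387 + 1.282) × √(2/20)] = 3.07 / (3.669 × 0.3162) = 2.65.
- Standard error of a two-arm difference = 2.65 × 0.3162 = 0.837.
- With no true effect and a scoring shift b in one arm, the pairwise false-positive rate = 1 − Φ(2.387 − b/SE) + Φ(−2.387 − b/SE).

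Section 7.1 also quotes an SD of 8 to 10 for the slope. That gives standard errors of 8 × 0.3162 = 2.53 and 10 × 0.3162 = 3.16, so the same formula is shown at those values too.

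| Assumed shift b | b / 3.07 | SD 2.65 | SD 8 | SD 10 |
|---|---|---|---|---|
| 0 | 0% | 1.7% | 1.7% | 1.7% |
| 0.5 | 16% | 3.8% | 1.9% | 1.8% |
| 1.0 | 33% | 11.7% | 2.6% | 2.3% |
| 1.5 | 49% | 27.6% | 3.8% | 3.0% |

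Whether a given shift matters depends heavily on an SD that the plan does not settle. The table shows the mechanism. It is not evidence that bias exists.

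**The case against.** The strongest reply is that the only explicit open-access route may carry no on-treatment uric acid. Sections 3.1 and 5.5 both point to no uric acid at Visit 4, and the list in 6.3 does not assign tests to visits. That is fair. It turns the Visit 4 route into a contradiction to be resolved, not an established leak.

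For Visit 6, a reader might infer that the result sits in a clinical record while the neurogram is being read. The documents do not support this: they say where the assay is done, but not who receives it, when, or when neurograms are scored. Nor could a Visit 6 result affect conduct during treatment, since the blood is drawn at the end of the six weeks. Only scoring and the remaining end-of-study measurements could be touched.

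A reader might also infer that about a third of the 100 subjects would be unblinded. That needs the size and spread of the uric acid fall, and neither is given. The expectation in section 1.3 of more than 90% enzyme inhibition is an argument from drug concentrations, and section 5.5 claims only an indirect measure of adherence.

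Finally, section 6.1 (study personnel) and Appendix 1 (procedure descriptions) were not available, so a masking rule there cannot be excluded. No available text shows renin results reaching investigators either; section 6.3 does not say where renin is assayed.

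What stands is that the routing and access that are described can expose an arm-specific marker to people involved in the primary outcome, and no available text prevents it.

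**Conclusion.** The point holds as a gap in protection: unblinding of the allopurinol arm is possible under the plan as written. The documents do not show that it occurred or would be widespread, and neither its extent nor any bias can be quantified from them. The losartan arm is not directly exposed by uric acid.

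The conclusion rests on two assumptions: that on-treatment uric acid separates allopurinol from the other arms well enough to be informative, as its use in section 5.5 implies, and that no masking rule sits in the sections not available. It is worth correcting because the remedy is cheap and protects the primary outcome. The mismatch between sections 3.1, 5.5 and 6.3 needs resolving in any case.

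**What to change.** 1. Reconcile sections 3.1, 5.5 and 6.3 so that uric acid is measured only at baseline and week 6, as 5.5 states, and split the pooled list in 6.3 by visit.
2. In 5.5, 6.3 and 9.4, state that post-randomisation uric acid is assayed in batch from the coded stored samples, or that the laboratory sends results only to the Pharmaceutical Research Center, which already holds the unblinding information. Release these results and plasma renin activity to investigators and scorers only after database lock. Align the unexpected-findings text in 6.5 with this.
3. In 3.2 or Appendix 1, state that neurograms are scored masked to subject ID, visit and laboratory results.
4. Leave creatinine and potassium open to investigators for safety, as now.

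The cost is protocol wording and a laboratory-routing instruction, with no extra staff or procedures. The downside is that biochemical adherence is known only at the end of the study; the drug diary remains available meanwhile. If such masking is already practised, the change only records it.
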